11.6.2.8 Performance Status

ECOG performance status ([Appendix L](#)) will be assessed at the times specified in the SoA ([Table 16](#) and [Table 17](#)) as follows:

- Screening
- Every Cycle Day 1
- EoT visit

11.6.2.9 Clinical Safety Laboratory Assessments

Clinical laboratory safety tests, including urine or serum pregnancy tests, will be performed in a licensed clinical laboratory according to local standard procedures. Sample tubes and sample sizes may vary depending on the laboratory method used and routine practice at the site. Additional safety samples may be collected if clinically indicated at the discretion of the Investigator. The date, time of collection, and results (values, units, and reference ranges) will be recorded on the appropriate eCRF.

Laboratory values will be repeated, confirmed, and followed up as appropriate.

Safety laboratory assessments will be performed at the timepoints specified in the SoA ([Table 16](#) and [Table 17](#)) Collection times begin from the start of the infusion.

Following SRC review of emerging data, the timing of laboratory safety assessment samples may be adjusted for subsequent cohorts. Additional sampling times may be added or removed if indicated by the emerging data.

11.6.2.9.1 COVID-19 Testing

COVID-19 tests will be conducted where appropriate and in accordance with local procedures. COVID-19 testing may include nucleic acid/PCR and/or serological approaches. This should be performed as follows:

- Screening: patients with a positive PCR test results must be antigen negative with confirmed IgG antibodies to COVID-19 to be able to start treatment

- At each cycle from Cycle 2 onwards Day 1: pre-infusion
- EoT visit

11.6.2.9.2 Viral Serology

A Hepatitis B, Hepatitis C, HIV, and CMV viral serology sample will be collected at screening. If a patient was found to have positive anti-HBC antibody and a negative HBsAg, a DNA PCR test will be done to determine eligibility criteria.

11.6.2.9.3 Pregnancy Test (Women of Childbearing Potential Only)

A urine/serum sample for a pregnancy test will be collected from all women of childbearing potential (defined in Section 5.3) as follows:

- Screening
- Day 1 of each treatment cycle: pre-infusion
- EoT visit

11.6.2.9.4 Clinical Chemistry

Blood samples for determination of clinical chemistry will be collected as specified in [Table 16](#) and [Table 17](#). Unscheduled samples may be collected if deemed clinically warranted, and results of unscheduled assessment should be recorded in the eCRF.

If an unscheduled ECG is performed for patient assessment, an electrolyte panel (ie, calcium, magnesium potassium) must be done. If clinically indicated, a troponin assay should coincide with this evaluation. Cardiac troponin I is preferred when available, however if not, cardiac troponin T is acceptable. To allow comparison with baseline, sites are requested to maintain consistency with the troponin assay used. Isolated troponin elevations are not sufficient to trigger dosing changes and should be evaluated in the context of other cardiac findings.

The following clinical chemistry tests will be performed ([Table 19](#)):

Table 19 Clinical Chemistry

Albumin	Cholesterol ^a	Magnesium
Alkaline phosphatase	C-reactive protein	Phosphate
Alanine aminotransferase	Creatinine	Potassium
Amylase ^b	Gamma-glutamyl transferase	Sodium
Aspartate aminotransferase	Glucose ^a	Triglycerides ^a
Bicarbonate	Glutamate dehydrogenase ^b	Total protein
Bilirubin (total and direct)	Lactate dehydrogenase	Chloride
Blood urea nitrogen	Lipase ^c	Uric acid
Calcium		

^a Fasting cholesterol, triglyceride and glucose values are not required. However, if non-fasting values are abnormal, a repeat sample should be obtained when the patient is fasting.

^b Glutamate dehydrogenase testing is optional, but should be performed where sites have the capability to perform the test locally.

^c Collected at screening, pre-infusion on each dosing day, and end of treatment visit.

NB. Refer to [Appendix E](#) if alanine amino transferase or aspartate aminotransferase $\geq 3 \times$ ULN together with total bilirubin $\geq 2 \times$ ULN.

ULN, upper limit of normal range.

Results for LFTs must be available and reviewed before infusion of study treatment throughout Cycle 1 and review of results is recommended before each administration of study treatment from Cycle 2 and beyond. Values must have returned to the patient's baseline before infusion of AZD0466.

Clinical chemistry, including creatine phosphokinase, should be performed for Part A and B according to the schedule below.

- Screening
- Pre-infusion on each dosing day
- 24 hours (± 2 hours) after each dosing
- EoT visit

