6.6 Dose Modification and Toxicity Management

AZD0466 may be withheld and the dose reduced due to haematological or non-haematological toxicities. In general, no AZD0466 dose modification is required if a patient experiences a Grade 1 or Grade 2 AE. However, AZD0466 should be modified or discontinued when the AEs described in this section are observed whether during ramp-up or once target dose is reached. Modifications based on cardiac AEs are described in Section 6.6.5.

Acceptable dose modifications shown in Table 4 are applicable during ramp-up and once target dose is reached. A maximum of 3 dose modifications are acceptable, except for CTCAE Grade 3 or 4 haemorrhage and any intracranial haemorrhage or haematoma, of which only one event is allowed. Also see Table 5, Table 6, Table 7, and Table 8.

Table 4 Dose Reduction Modifications

Cohort level	AZD0466 dose	Dose reductions		
		1 lower dose	2 lower doses	3 lower doses
DL-1	37.5 mg	--	--	--
	75 mg	37.5 mg	--	--
	150 mg	75 mg	37.5 mg	--
DL1	75 mg	37.5 mg	--	--
	150 mg	75 mg	37.5 mg	--
	300 mg	150 mg	75 mg	37.5 mg
DL2	150 mg	75 mg	37.5 mg	--
	300 mg	150 mg	75 mg	37.5 mg
	600mg	300 mg	150 mg	75 mg
DL3	300 mg	150 mg	75 mg	37.5 mg
	600 mg	300 mg	150 mg	75 mg
	1200 mg	600 mg	300 mg	150 mg
DL4	600 mg	300 mg	150 mg	75 mg
	1200 mg	600 mg	300 mg	150 mg
	2400 mg	1200 mg	600 mg	300 mg
DL5 ^a	1200 mg	600 mg	300 mg	150 mg
	2400 mg	1200 mg	600 mg	300 mg
	3600 mg	2400 mg	1200 mg	600 mg
DL6 ^a	2400 mg	1200 mg	600 mg	300 mg
	3600 mg	2400 mg	1200 mg	600 mg
	5400 mg	3600 mg	2400 mg	1200 mg
DL6 – alternative ramp-up ^b	1400 mg	600 mg	300 mg	150 mg
	2800 mg	1200 mg	600 mg	300 mg
	5400 mg	3600 mg	2400 mg	1200 mg

^a AZD0466 doses shown are illustrative. Actual doses will not exceed a 2-fold increase of a dose declared tolerable by the SRC, or the maximum feasible dose as specified in Section 11.4.7.5.

^b SRC to determine ramp-up as well as target dose.

DL, dose level; SRC, Safety Review Committee

While on study, patients diagnosed with COVID-19 and are thought to be receiving clinical benefit as deemed by the investigator may continue to receive AZD0466; however, must pause treatment if they meet pause or discontinuation criteria for dose modifications based on haematological parameters (Section 6.6.1, neutropenia), or CTCAE Grade 2 or higher non-haematological toxicities (Section 6.6.3), which would include pneumonia or other infectious complications.

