6.6.4 Dose Modifications for Hepatotoxicity

AZD0466 dosing should be modified if a patient with normal or abnormal baseline liver function experiences a clinically significant and/or unacceptable change in hepatic biochemistry (including a DLT) described in [Table 8](#) that is considered by the Investigator to be related to study treatment and not attributable to the disease (or to disease-related processes) under investigation.

Table 8 Dose Modification for Hepatotoxicity

Event	Occurrence	Action with AZD0466
For patients with normal baseline liver function: ALT and/or AST > 5 × ULN and ≤ 8 × ULN without concomitant elevation in bilirubin, which return to baseline within 7 days OR For patients with abnormal baseline liver function: ALT and/or AST > 5 × baseline and ≤ 8 × baseline or ALT and/or AST > 7 × ULN and ≤ 10 × ULN, (whichever is lower in × ULN), without concomitant elevation in bilirubin, which return to baseline levels within 7 days	First occurrence	
 Withhold AZD0466 until values return to CTCAE Grade ≤ 1 or baseline. Restart AZD0466 at same dose level if at target or dose escalate if at ramp-up.
	Second occurrence	
 Withhold AZD0466 until values return to CTCAE Grade ≤ 1 or baseline. Restart AZD0466 at one lower dose if at target or consider to discontinue if at ramp-up.
	Third occurrence	
 Withhold AZD0466 until values return to CTCAE Grade ≤ 1 or baseline. Discontinue if at ramp-up. If at target dose: Restart AZD0466 at one lower dose than the current dose if all values resolve to baseline or Grade ≤ 1 within 7 days and there is clear evidence of clinical benefit. A Q2W schedule may be considered. Discontinue AZD0466 if the above criteria are not met.

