For patients with normal baseline liver function: ALT and/or AST > 8 × ULN and ≤ 20 × ULN without concomitant elevation in bilirubin, which return to baseline or Grade 1 levels within 14 days OR For patients with abnormal baseline liver function: ALT and/or AST > 8 × baseline and ≤ 20 × baseline or ALT and/or AST > 10 × ULN and ≤ 20 × ULN, (whichever is lower in x ULN), without concomitant elevation in bilirubin, which return to baseline or Grade 1 levels within 14 days	First occurrence	
 Withhold AZD0466 until values return to CTCAE Grade ≤ 1 or baseline. Consider to discontinue if at ramp-up. If at target dose: Restart AZD0466 at one lower dose than the current dose.
	Second occurrence	
 Withhold AZD0466 until values return to CTCAE Grade ≤ 1 or baseline. Discontinue if at ramp-up and not previously stopped. If at target dose: Restart AZD0466 at one lower dose than the current dose and consider Q2W dosing schedule.
	Third occurrence	
 Withhold AZD0466 until values return to CTCAE Grade ≤ 1 or baseline. Restart AZD0466 at 2 lower dose levels than current dose and resume on a Q2W schedule, if all values resolve to baseline or CTCAE Grade ≤ 1 within 14 days and there is clear evidence of clinical benefit. Discontinue AZD0466 if the above criteria are not met.

Table 8 Dose Modification for Hepatotoxicity

Event	Occurrence	Action with AZD0466
For patients with normal baseline liver function: ALT and/or AST $\geq 3 \times$ ULN with concomitant elevation in bilirubin $\geq 2 \times$ ULN OR For patients with abnormal baseline liver function: ALT and/or AST $\geq 3 \times$ baseline with concomitant elevation in bilirubin $\geq 2 \times$ baseline	Any occurrence	
 Discontinue AZD0466, refer to Appendix E for process to follow in order to identify and appropriately report episodes of potential Hy's Law.
ALT and/or AST $> 20 \times$ ULN	Any occurrence	
 Discontinue AZD0466.

ALT, alanine aminotransferase; AST, aspartate aminotransferase; CTCAE, common terminology criteria for adverse events; ULN, upper limit of normal; Q2W, every 14 days

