11.4.7.2 Dose-limiting Toxicity

Any event that meets the DLT criteria in the opinion of the Investigator should be reported to the Medical Monitor within 24 hours of knowledge of the event. Events will be assessed for DLT criteria according to the CTCAE National Cancer Institute (NCI) v5.0 (Section [8.3.2](#)) except for TLS, which will be assessed for DLT criteria using the Howard modification of Cairo-Bishop criteria ([Appendix G](#)). Toxicity that is clearly and directly related to the underlying malignancy or to an extraneous cause is excluded from the definition of a DLT. A DLT will be defined as the occurrence of any of the following:

- Any CTCAE Grade 3 non-haematological toxicity lasting > 7 days OR any CTCAE Grade 4 non-haematological toxicity, with the exception of:
 - CTCAE Grade 4 nausea, vomiting, or diarrhoea lasting < 7 days in the absence of maximum supportive therapy,
 - Elevation in serum amylase and/or lipase without clinical or radiographic evidence of pancreatitis,
 - CTCAE Grade 3 fatigue, asthenia, fever, anorexia, or constipation.
- Any other cardiac findings of CTCAE Grade ≥ 2 if considered by the Investigator to be clinically significant.
- AZD0466 should be permanently discontinued if a CTCAE Grade ≥ 3 cardiac AE of any duration occurs at any time during study treatment, if considered by the Investigator to be related to study treatment.
- AZD0466 should be permanently discontinued if liver function test abnormalities meets Hy's Law (HL) or Potential Hy's Law (PHL) criteria, and considered by the Investigator to be related to study treatment (see [Appendix E](#)).
- Prolonged myelosuppression: as myelosuppression and cytopenias are expected outcomes of leukaemia treatment, only the criteria defined below will be a DLT:
 - Lack of haematological recovery (ANC remaining $<0.5 \times 10^9/L$, platelets remaining $< 50 \times 10^9/L$) in the absence of active leukaemia in bone marrow (blasts $< 5\%$) and with marrow hypocellularity at $< 5\%$ by Day 42.
- Cairo-Bishop Grade ≥ 3 Clinical TLS ([Appendix G](#)) that occurs despite protocol-recommended management.
- Cairo-Bishop Laboratory TLS ([Appendix G](#)) with metabolic abnormalities that do not resolve within 5 days despite protocol-recommended management.
- Any other toxicity that
 - is greater than at baseline, is clinically significant and/or unacceptable, and is judged to be a DLT by the SRC, or
 - results in a disruption of dosing schedule of more than 21 days.

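### The liver rules conflict: infusion requires return to baseline in 11.6.2.9.4 but only Grade 1 in Table 8, and for patients with abnormal baseline the combined stopping criterion is scaled to baseline in Table 8 but to ULN in 11.4.7.2

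*Protocol*

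**What the plan says.** **Before an infusion.** Protocol 11.6.2.9.4 requires liver results to be available and reviewed before dosing throughout Cycle 1. For later cycles it says only that "review of results is recommended before each administration of study treatment from Cycle 2 and beyond". The next sentence is mandatory, with no Grade 1 alternative and no cycle limit: "Values must have returned to the patient's baseline before infusion of AZD0466". Section 12.6.2.9.4 carries the same sentence for Module 2.

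**After a liver event.** Table 8 in 6.6.4 covers two tiers of isolated ALT/AST elevation. In both, the action for every occurrence begins: "Withhold AZD0466 until values return to CTCAE Grade ≤ 1 or baseline". Treatment may then restart, subject to the row's other conditions.

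**Combined ALT/AST and bilirubin elevation.** Table 8 discontinues AZD0466 at any occurrence, in two versions. For normal baseline the limits are 3 x ULN and 2 x ULN. For abnormal baseline they are 3 x baseline and 2 x baseline. Section 11.4.7.2 includes in its DLT list: "AZD0466 should be permanently discontinued if liver function test abnormalities meets Hy's Law (HL) or Potential Hy's Law (PHL) criteria", where the investigator considers the abnormality related, and points to Appendix E. Appendix E 2 defines both terms by 3 x ULN with 2 x ULN and has no baseline-scaled version.

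**The concern.** Hepatotoxicity is an important potential risk (2.2) and an AESI (8.3.12), and transient transaminase abnormalities are an anticipated on-target effect (2.1.2). In Module 2, abnormal liver tests are the acknowledged overlap with voriconazole (12.1.6). These rules are therefore likely to be used.

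Where two sections give different answers to the same laboratory result, sites will hold or stop treatment differently. That affects patient protection. It also affects two quantities in the analysis: the number of target doses received, which decides DLT-evaluability, and the important protocol deviations.

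**Working it through.** No sample-size or error-rate figure is involved. The check sets the passages side by side and converts the limits to multiples of ULN.

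**1. Restart, upper tier (above 8 and up to 20 x ULN, normal baseline).** Table 8 defines this event as one that recovers, within 14 days, to either baseline or Grade 1. Its action uses the same alternative. Take a patient who peaks in this tier, is back at Grade 1 on the dosing day and is still above baseline. Table 8 permits the restart. Section 11.6.2.9.4 does not, because a restart is an infusion.

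**2. Restart, lower tier (above 5 and up to 8 x ULN).** The event is defined by return to baseline within 7 days, while the action accepts Grade 1. Table 8 is inconsistent within this row, before any comparison with 11.6.2.9.4.

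**3. Precedence.** Section 11.4.6 sends Module 1 dose modification to core 6.6, whereas 11.6.2.9.4 is itself Module 1 text. The rule in 5.1 that the more stringent module criterion prevails concerns inclusion criteria only. Neither settles the matter.

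**4. Discontinuation, abnormal baseline.** Inputs are Table 3 (ALT/AST up to 2.5 x ULN; bilirubin up to 1.5 x ULN, or 3 x ULN in Gilbert's syndrome), Table 8 and Appendix E 2. The Table 8 limits are 3 x baseline ALT/AST and 2 x baseline bilirubin. All figures are x ULN.

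| Baseline ALT/AST; bilirubin | Table 8 triggers at | Appendix E triggers at |
|---|---|---|
| 1.5; 1.0 | 4.5; 2.0 | 3; 2 |
| 2.0; 1.2 | 6.0; 2.4 | 3; 2 |
| 2.5; 1.5 (eligibility limit) | 7.5; 3.0 | 3; 2 |
| 2.5; 3.0 (limit in Gilbert's) | 7.5; 6.0 | 3; 2 |
| 1.5; 0.5 (only ALT abnormal) | 4.5; 1.0 | 3; 2 |

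The last row assumes that raised ALT alone counts as abnormal baseline liver function. There the mismatch runs the other way on bilirubin, where Table 8 triggers at the lower value.

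**5. Worked case.** Baseline AST is 2.0 and bilirubin 1.2 x ULN, both eligible. On study they are 4.0 and 2.1 x ULN on the same day, judged related.
- Appendix E: 4.0 is at least 3 and 2.1 is at least 2, so 11.4.7.2 requires permanent discontinuation.
- Table 8 combined row: 4.0 is below 6.0 and 2.1 is below 2.4, so it is not met.
- Table 8 lower isolated tier: it starts at the lower of 5 x 2.0 = 10 and 7 x ULN, which is 7, so it is not met. The upper tier and the row above 20 x ULN are not met either.

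Sections 6.6.4 and 11.4.7.2 both require relatedness, so causality does not explain the difference.

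**6. Consequence for the analysis sets.** Without a DLT, a patient needs 3 of the 4 target doses on Days 8, 15, 22 and 29 (11.4.7.1; SAP Table 5). Two held target doses leave 4 - 2 = 2, so the patient is not DLT-evaluable.

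**The case against.** Several objections are sound and limit the point.

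- **Scope of Table 8.** A reader might infer that Table 8 as a whole judges the combined criterion against baseline. It does not. The normal-baseline version is identical to Appendix E, and only the abnormal-baseline version differs.
- **DLT count.** It is tempting to say that the conflict adds a DLT and, for example, moves Table 10 from escalate at 1 of 6 to stay at 2 of 6. The documents do not support this. Table 8 defines no DLT, 6.7 refers DLTs to Module 1, and SAP 4.14.2 cites 11.4.7.2 alone. The worked patient's DLT status is the same whatever Table 8 says.
- **Continue versus stop.** Table 8 does not tell the site to keep dosing in the gap. It has no row for that patient, so a site that also reads 11.4.7.2 would stop. The difficulty is that a site using Table 8, the designated dose-modification table, finds a different criterion there.
- **Lower-tier example.** A patient who peaks at 6 x ULN and falls to 2 x ULN is a weak illustration of the restart conflict, because that tier's event is itself defined by return to baseline. The documents also print no CTCAE limits for ALT/AST.
- **Section 6.6.** Its sentence "In general, no AZD0466 dose modification is required if a patient experiences a Grade 1 or Grade 2 AE" is a general default, followed at once by an exception for the listed events. It does not contradict a specific liver check.
- **Cycle 1 reading.** The baseline sentence follows one that mandates review only in Cycle 1, so it may have been meant for Cycle 1. This narrows the scope without removing the conflict, since Table 8 also applies in Cycle 1. If the sentence applies to all cycles, a mandatory condition from Cycle 2 rests on a review that is only recommended.
- **Appendix E.** It states that it is not a full guide to managing raised liver tests, and E 6 deals with patients who already met its criteria before treatment. E 6 does not help here, because ALT/AST within the eligibility limit of 2.5 x ULN cannot reach 3 x ULN at screening. The objection does show that the Appendix E reporting definition should be left alone.

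**Conclusion.** Both contradictions stand in the text, and no stated hierarchy resolves them.

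The restart conflict applies to any patient recovering to Grade 1 but not to baseline, most clearly in the upper isolated tier, in both modules. The discontinuation conflict applies only to patients with abnormal baseline liver function. At the general eligibility limits it is the difference between 7.5 and 3.0 x ULN in Table 8 and 3 and 2 x ULN through 11.4.7.2.

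The documents give no prevalence for abnormal baseline, so the number of patients affected is unknown. Such patients can be enrolled, and nothing more is claimed.

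The consequences are inconsistent holding and stopping for an AESI, possible loss of DLT-evaluability, and uncertainty over SAP Deviation 2 (4.6.2.1), which captures patients who fulfilled a stopping criterion but stayed on AZD0466. The worked patient, if kept on treatment, is a deviation under 11.4.7.2 and not under Table 8. No effect on the DLT definition or on the Table 10 decisions is shown. The worked case assumes same-day elevations and investigator-judged relatedness.

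**What to change.** 1. Reconcile 11.6.2.9.4 and 12.6.2.9.4 with Table 8 so that one recovery criterion governs infusion, and remove the mismatch between event definition and action in the lower tier of Table 8.
2. Bring the wording on liver-test review from Cycle 2 into line with the strength of that criterion, and state which cycles it covers.
3. Reconcile the abnormal-baseline combined row of Table 8 with 11.4.7.2 so that one discontinuation criterion applies. The Appendix E reporting definition need not change.
4. Because the SAP records that the study has been terminated, state in the protocol deviations specification which text defines Deviation 2 for these patients.

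The clinical team chooses the criteria. The cost is wording in a few places. Clinical chemistry is already scheduled before infusion on every dosing day, so no new samples are needed.

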11.6.2.9.5 Amylase and Lipase

Amylase and lipase will be collected for Part A and Part B according to the schedule below.

- Screening
- Pre-infusion on each dosing day
- EoT visit

11.6.2.9.6 Complete Blood Count with Differential CCI

Complete blood counts with differential CCI (Table 20) will be collected for Part A and Part B. Part of the blood sample collected for CBC will be used for peripheral blood smears as detailed in Section 11.6.1.

Table 20 Haematology Assessments

Absolute leucocyte differential count: neutrophils, lymphocytes, monocytes, basophils, eosinophils	CCI
Blood (B)-haemoglobin	Haematocrit
Leucocytes	Platelet count

Collection times for Part A and Part B are indicated below (collection time begins from start of infusion).

- Screening
- Cycle 1 Day 1: pre-infusion, end of infusion (+10 minutes), 6 hours (± 30 minutes) after the start of the infusion
- Cycle 1 Day 2: 24 hours (± 2 hours) after the Day 1 infusion
- Cycle 1 Day 4: pre-infusion, end of infusion (+10 minutes)
- Cycle 1 Day 5: 24 hours (± 2 hours) after the Day 4 infusion
- Cycle 1 Day 8: pre-infusion, at the end of infusion (+10 minutes), 2 hours (± 30 minutes) 6 hours (± 30 minutes), 9 hours (± 1 hour) after the start of the infusion
- Cycle 1 Day 9: 24 hours (± 2 hours) after the Day 8 infusion
- Cycle 1 Day 15: pre-infusion
- Cycle 1 Day 16: 24 hours (± 2 hours) after the Day 15 infusion
- Cycle 1 Day 22: pre-infusion
- Cycle 1 Day 23: 24 hours (± 2 hours) after the Day 22 infusion
- Cycle 1 Day 29: pre-infusion
- Cycle 1 Day 30: 24 hours (± 2 hours) after the Day 29 infusion (and at disease assessment if disease assessment is not on Day 30)
- At each cycle from Cycle 2 onwards: pre-infusion on each dosing day
- At each cycle from Cycle 2 onwards: 24 hours (± 2 hours) after each dosing
- At each disease assessment
- EoT visit

